4.4. Multiple Testing and Comparisons

No adjustment will be made for the testing of multiple endpoints.

4.5. Adjustment for Covariates

Not applicable.

4.6. Subgroups

Due to small sample size, no subgroups will be identified for this study.

4.7. Presentation Over Time

For endpoints that are collected serially over time, assessments/test values will be assigned to a specific timepoint (e.g., study week) based upon the electronic case report form (eCRF) page on which the assessments/test values were reported.

For an efficacy endpoint, an unscheduled/early termination assessment may be used in the summary by timepoint if the unscheduled assessment was within 2 weeks of a missing scheduled assessment. If unscheduled assessments are collected with multiple dates or times within a given visit, the result closest to the scheduled visit date will be used for summary presentations. If 2 measurements have the same distance to the expected date, the earlier assessment value will be used.

For safety endpoints, unscheduled assessments will not be included in the summary by timepoint.

4.8. Algorithm, Computation and Definition of Derived Variables

Day 1

For eteplirsen treated patients, Day 1 will be defined as the date of the first eteplirsen administration. For untreated patients, Day 1 will be defined as the date of the last Screening/Week 1 assessment.

Study Day

Study day will be defined as Event Date – Day 1 + 1, if Event Date is on or after Day 1; otherwise, as Event Date – Day 1, if Event Date precedes Day 1.

Duration on Study

Duration on study will be calculated as the duration in weeks from Day 1 to the date of study completion/discontinuation as recorded on the END OF STUDY eCRF (if completed) or the date of the last study assessment or procedure. The duration in weeks calculated above will then be categorized to one of the following intervals: < 24, 24 to < 48, 48 to < 72, 72 to 96, ≥ 96 .

Duration of Treatment

For treated patients, duration of eteplirsen treatment will be calculated as the duration in weeks from the date of first dose of eteplirsen to the date of the last eteplirsen administration as recorded on the STUDY DRUG ADMINISTRATION eCRF plus 7 days (or 1 week), i.e., $(\text{Last dose date} - \text{first dose date} + 7)/7$. The duration in weeks calculated above will then be categorized to one of the following intervals: < 24, 24 to < 48, 48 to < 72, and ≥ 72 .

Baseline

For treated patients, baseline will be defined as the last value prior to the first dose of eteplirsen administration. For untreated patients, baseline will be defined as the last value on or before the Day 1 date.

CCI

CCI [REDACTED]
[REDACTED]
[REDACTED]
[REDACTED]
[REDACTED]
[REDACTED]
[REDACTED]

CCI [REDACTED]
[REDACTED]
[REDACTED]
[REDACTED]
[REDACTED]
[REDACTED]
[REDACTED]
[REDACTED]
[REDACTED]

Planned Dose and Overdose

The body weight-based planned dose was calculated based on most recent weight of previous visits. When calculating the planned dose, the body weight is rounded to single decimal using conventional rounding rules. While in preparing actual dose, an unconventional rule is applied for calculating the volume of the concentrated drug (50 mg/ml) in milliliter. Any volume number 0.1 or above is rounded up, e.g. 25.14 ml is rounded up to 26 ml, and any volume number below 0.1 is rounded down, e.g. 25.09 ml is round up to 25 ml. The overdose is defined as any actual dose >10% above the planned body weight-based dose.

Treatment-emergent Adverse Event (TEAE)

For treated patients, an AE will be considered treatment-emergent if it starts in the time period starting with the initiation of the first dose of eteplirsen and ending 28 days after the last dose of eteplirsen. For untreated patients, an AE will be considered treatment-emergent if it starts on or after the Day 1 date.

Treatment-related Adverse Event

A treatment-related AE is any AE reported on the ADVERSE EVENTS eCRF that is marked as definitely related, or probably/possibly related to study drug.

Treatment Emergent Laboratory Abnormality

CCI [REDACTED]

[REDACTED]

[REDACTED]

[REDACTED]

[REDACTED]

[REDACTED]

[REDACTED]

[REDACTED]

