14.8.2.1. Adverse Events

For eteplirsen-treated patients, only treatment-emergent adverse events (TEAEs) will be summarized. Non-emergent events will be recorded in data listings. For all AE tables, the number and percent of patients reporting AEs (grouped by the Medical Dictionary for Regulatory Activities [MedDRA] System Organ Class [SOC] and Preferred Term [PT]) will be summarized. In general, tables will have events categorized into all TEAEs and treatment-related TEAEs.

Multiple occurrences of the same AE (at the PT level) in the same patient will be counted only once in frequency tables. If a patient experiences multiple episodes of the same event with different relationship/severity, the event with the strongest relationship and maximum severity to IP will be used to summarize AEs by relationship and severity.

Treatment-related TEAEs will be defined as those that the Investigator considers possibly/probably or definitely related to the IP.

The following summary tables will be produced:

- TEAEs
- TEAEs by severity
- Treatment-related TEAEs
- Treatment-related TEAEs by severity
- Treatment-emergent SAEs
- Death
- Overdose

In addition, all SAEs, regardless of their treatment-emergent status will be summarized by SOC and PT.

For untreated patients, AEs and SAEs that first occur or worsen in severity after the study enrollment will be summarized in the same fashion as the TEAEs and treatment-emergent SAEs for the eteplirsen-treated group. In addition, all SAEs, regardless of time of occurrence, will be summarized by SOC and PT.

For all patients, the following listings will be produced:

- All AEs, including non-treatment emergent AEs and TEAEs
- AEs leading to discontinuation
- SAEs

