5.8.1 Adverse Events

In general, only TEAEs will be summarized (for untreated subjects, AEs that first occur or worsen in severity after the study enrollment are considered treatment-emergent). Non-treatment-emergent adverse events will be recorded in the data listings. Unless noted otherwise, for all AE tables, the number and percentage of patients reporting AEs will be grouped using the MedDRA, SOC, and PT and summarized for treated patients, untreated patients, and overall.

An overall summary table of adverse events will be produced and will include the frequency count and percentage of patients with

- TEAE
- Treatment-related TEAE
- Severe TEAE
- Treatment-Emergent SAE
- Treatment-Emergent Related SAE
- TEAE leading to discontinuation of study drug
- TEAE leading to death

The number of events at each severity level (mild, moderate, severe) will also be included.

Multiple occurrences of the same AE (at the PT level) in the same patient will be counted only once in frequency tables. If a patient experiences multiple episodes of the same event with a different relationship/severity, the event with the strongest relationship or maximum severity to investigational drug product will be used to summarize AEs by relationship and severity.

The following summary tables will be produced:

- TEAEs by SOC and PT
- TEAEs by SOC, PT and severity
- TEAE by PT in descending frequency
- Treatment-related TEAEs by SOC and PT
- Treatment-related TEAEs by SOC, PT, and severity
- Treatment-related TEAEs by PT in descending frequency
- Treatment-Emergent SAEs by SOC and PT
- Treatment-related Treatment-Emergent SAEs by SOC and PT
- TEAEs leading to treatment discontinuation by SOC and PT
- TEAEs leading to death by SOC and PT
- Non-serious TEAEs by SOC and PT, displaying both number of subjects and number of events

The following listings will be produced:

- All AEs
- AEs leading to treatment discontinuation
- SAEs

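### SAP 4.8 defines a treatment-emergent AE by start date alone, while SAP 5.8.1 also counts worsening but only for untreated patients; the AE tables need one definition

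*SAP*

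**What the plan says.** SAP 4.8 gives two definitions, both based on onset. For the treated group: "For treated patients, an AE will be considered treatment-emergent if it starts in the time period starting with the initiation of the first dose", with the window closing 28 days after the last dose. For the other group: "For untreated patients, an AE will be considered treatment-emergent if it starts on or after the Day 1 date". Neither mentions an event that was already present and became more severe.

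SAP 5.8.1 then adds, in parentheses: "for untreated subjects, AEs that first occur or worsen in severity after the study enrollment are considered treatment-emergent". It has no matching clause for treated patients. Protocol 14.8.2.1 has the same asymmetry. It says "For untreated patients, AEs and SAEs that first occur or worsen in severity after the study enrollment will be summarized" alongside the treated group's TEAEs, but for the treated group only "For eteplirsen-treated patients, only treatment-emergent adverse events (TEAEs) will be summarized", without defining the term.

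The classification decides where an event is shown. AE tables are generally limited to TEAEs and are "summarized for treated patients, untreated patients, and overall". For the rest, "Non-treatment-emergent adverse events will be recorded in the data listings".

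For SAEs the Protocol adds a safeguard: "all SAEs, regardless of their treatment-emergent status will be summarized by SOC and PT". The table list in SAP 5.8.1 contains only treatment-emergent SAE tables.

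**The concern.** Two sections of one SAP give a programmer different instructions for the same untreated patient. The treated group, which carries the primary safety objective, has the narrower rule wherever a rule is visible.

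Events before first dose are foreseeable. Protocol 12.1 collects AEs from consent, the Screening/Baseline period lasts up to 5 weeks, and treated patients have a muscle biopsy in it. If such an event worsens on eteplirsen and stays on its original record, its start date precedes the first dose and it fails the 4.8 test. It is then missing from the TEAE tables, including those for severe, related and treatment-emergent serious events, and from the special-interest and additional-review tables in SAP 5.8.2 and 5.8.3, which are also built on TEAEs. The safety endpoint is incidence, and a listing does not give an incidence.

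**Working it through.** The plan states no figure on this point, so the check applies the rules to cases and then works out what one patient weighs.

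**Cases**

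| Case | SAP 4.8 | SAP 5.8.1 | Result |
|---|---|---|---|
| Treated; starts between first dose and 28 days after last dose | TEAE | no separate rule | in tables |
| Treated; starts before first dose, worsens on drug, same record | not a TEAE | no worsening clause | listings only |
| Treated; as above, but worsening entered as a new record with its own onset | TEAE | no separate rule | in tables |
| Untreated; starts on or after Day 1 | TEAE | TEAE, if enrollment means Day 1 | in tables |
| Untreated; starts before Day 1, worsens later, same record | not a TEAE | TEAE | sections conflict |

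The second row is the gap, the third shows what it depends on, and the fifth is a contradiction in the text. If 5.8.1 wins in the fifth row, the overall column pools patients classified under two rules.

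**Reference dates for untreated patients**

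- SAP 4.8: on or after Day 1, with no end point.
- SAP 5.8.1: after study enrollment.
- SAP 4.2.2 (partial dates): after Day 1 and within a day of the last visit or, alternatively, on or after a qualifying visit that is not defined.
- Protocol section 3, footnote b, makes the last Screening/Week 1 assessment the study start date. SAP 4.8 uses the same date as Day 1.

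The different names are therefore probably a wording fault. The end point does differ between 4.8 and 4.2.2.

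**All-SAE table**

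Protocol 14.8.2.1 requires it for both groups. SAP 5.8.1 does not list it. No visible bullet in SAP 6.1 reports a change, though some bullets are redacted, and 6.1 closes by saying that nothing else is altered.

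**Weight of one patient where a row changes (1/N)**

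- Treated, planned N of 20 (SAP 3.3): 1/20 = 5.0 points. The actual number is not given; for an assumed 15 to 25, 1/15 = 6.7 to 1/25 = 4.0 points.
- Untreated, 7 enrolled (SAP 6.1): 1/7 = 14.3 points if all 7 are in the Full Set. SAP 4.3 also requires an assessment after enrollment, so the denominator could be smaller.
- Overall: 1/(20 + 7) = 1/27 = 3.7 points; with 15 to 25 treated, 1/22 = 4.5 to 1/32 = 3.1 points.

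The period in which such an event can first be recorded is at most 5 of about 105 weeks, 5/105 = 4.8% of participation. That is the length of a window, not a risk.

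**The case against.** The strongest reply is that the loss for treated patients depends on a recording rule that the reader cannot see. Protocol 12.2.1 treats a baseline abnormality that worsens as an AE. If sites enter that worsening with its own onset date, SAP 4.8 already captures it. The CRF Completion Guidelines, which are not among the documents, may require this. This stands: the gap is possible, not shown. It does not remove the conflict between 4.8 and 5.8.1. Nor does either document say which onset date to record or require a new record when an AE already recorded gets worse.

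A second reply is that a worsening rule may be hard to program. Protocol 12.4 asks for onset, resolution and severity, but not for the date of a change in severity. This also stands, and it is why the fix needs a record review and a bounded sensitivity table.

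A third reply is that little depends on it. Safety analysis is descriptive, SAP 6.1 rules out a direct comparison between the groups, and the event remains in the all-AE listing and, where applicable, the listings of SAEs and of AEs leading to treatment discontinuation. All of this is correct and limits the size of the point.

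Three stronger readings are tempting, and the documents do not support them. A reader might infer that the safety tables as a whole understate harm, but laboratory, vital-sign, ECG and ECHO summaries do not use the AE definition, and no frequency of pre-dose events that worsen is given. A reader might infer a biased contrast between the groups, but none is planned. A reader might infer that the all-SAE table was deliberately dropped, but absence from a list does not prove that, and the redactions in 6.1 prevent checking.

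**Conclusion.** The point holds as a definition fault that should be corrected before database lock. For untreated patients, SAP 4.8 and 5.8.1 cannot both be followed. For treated patients, the visible text has no route into the TEAE-based AE tables for a pre-dose AE that worsens on drug, provided the worsening is not opened as a new record. The missing all-SAE table is a separate discrepancy with the Protocol. It matters here because that table would have shown such an event if it was serious.

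The effect is confined to descriptive incidence, and how often it occurs cannot be derived. A row changes only if the patient has no other qualifying event at that level. The row for any TEAE may therefore not move, while rows by preferred term, severity or relatedness can. The 5.0-point figure assumes the planned 20 treated patients, and the 14.3-point figure assumes that all 7 enrolled untreated patients are analysed.

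**What to change.** 1. In SAP 4.8, use one definition for both groups: an AE is treatment-emergent if it starts, or becomes more severe than it was before first dose (treated) or before Day 1 (untreated), within the existing window. For treated patients that window runs from first dose to 28 days after the last dose. For untreated patients it opens on Day 1. Choose one end point for them, since 4.8 has none and 4.2.2 allows a day after the last visit.
2. Make SAP 5.8.1 and the partial-date rule in 4.2.2 refer to that definition, with Day 1 replacing both study enrollment and qualifying visit.
3. Before database lock, review AEs that were ongoing at first dose or Day 1 and identify those that worsened. Where a worsening cannot be dated, add a sensitivity table that counts those AEs as treatment-emergent, labelled as an upper bound.
4. Restore the all-SAE table to SAP 5.8.1, or list its removal in SAP 6.1.

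The cost is wording in three SAP sections, one SAE table or one line in 6.1, and a record review in about 27 patients (20 planned plus 7 enrolled). TEAE counts may rise slightly. The sensitivity table, if needed, overstates incidence because it also counts ongoing events that may not have worsened within the window.

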4.9. Programming Conventions

This section details general conventions to be used for the production of tables, figures and listings. Departures from these general conventions will be specified in appropriate sections.

- For continuous or quantitative variables, mean and median values will be formatted to 1 more decimal place than the measured value on the eCRF. Standard deviation and standard error values will be formatted to 2 more decimal places than the measured value on the eCRF. Minimum and maximum values will be presented with the same number of decimal places as the measured value on the eCRF. Percentages will be presented with 1 decimal place.
- For categorical variables, the number and percentage of a category will be presented in the form XX (YY%), where the percentage is YY.
- Percentages of patients with laboratory toxicities will be based on nonmissing values unless stated otherwise.
- Study Day will appear in the data listings as appropriate.
- Date variables will be formatted as DDMMYYYY for presentation.
- SAS® Version 9.4 or higher will be the statistical software package used for all analyses unless otherwise specified.
- The Clinical Data Interchange Standards Consortium (CDISC) Analysis Data Model Implementation Guide (ADaMIG) V1.0 for preparing data sets will be used for this study.
- The CDISC Study Data Tabulation Model Implementation Guide (SDTMIG) V3.2 for preparing data sets will be used for this study.
- Tables, figures, and listings will be presented in landscape orientation.
- Listings will be sorted by treatment, patient and then assessment or event start date unless otherwise specified.

5. STATISTICAL ANALYSES

5.1. Patient Disposition

The number of patients enrolled, the number in the safety population, the number randomized to muscle biopsy, the duration of the study (weeks) [both continuous and categorical interval summaries], the number and percentage of patients completing the study through Week 96 (i.e., completers), and the number and percentage of patients prematurely discontinuing before Week 96 will be summarized. Reasons for premature discontinuation will also be summarized. All analyses will be performed by treatment group.

Patient eligibility will be presented in a listing.

5.2. Demographics and Baseline Characteristics

Demographic characteristics including age (years), race, ethnicity, and baseline characteristics including height (cm), weight (kg), body mass index (BMI; kg/m²), time since DMD diagnosis (months) to Baseline, corticosteroid type (Deflazacort or Prednisone), corticosteroid frequency (continuous versus intermittent), mutation type(s), and duration of prior corticosteroid treatment (months) to Day 1 will be summarized by treatment group. Demographic data and baseline characteristics will also be presented in data listings.

5.3. Prior and Concomitant Medications

Concomitant medications will be coded by preferred term (PT) using the most recent World Health Organization (WHO) Drug Dictionary (WHODRUG, 01DEC2013). The number and percentage of patients in the safety population taking concomitant medications will be tabulated by Anatomical Therapeutic Chemical (ATC) classification, pharmacological subgroup, and WHO drug PT by treatment group. At each level of summarization, a patient is counted once if he/she reported 1 or more medications at that level.

All prior medications and concomitant medication will be presented in data listings.

5.4. Medical History

Medical history data for the safety set will be presented in data listings.

5.5. Physiotherapeutic Interventions

A listing of all physiotherapeutic interventions will be provided.

5.6. Protocol Deviations

A listing of major protocol deviations will be provided. The protocol deviations will be identified based on a review of the study data prior to the database lock and will include the nature of the deviation (e.g., inclusion/exclusion, prohibited therapies).

5.7. Exposure to Study Drug

The total number of infusions received, cumulative amount of drug received (mg), total volume of drug administered (mL), duration on eteplirsen in 24-week intervals, and the continuous number of weeks on eteplirsen will be summarized for all eteplirsen-treated patients. Dosing information will be provided in a data listing.

A listing of patients with overdose will be generated.

5.8. Safety Analyses

Safety analyses will be descriptive in nature. Safety analyses will include summaries of the following:

- The type, frequency, severity, timing, and relationship to the investigational drug product of AEs, SAEs, and discontinuations due to AEs. Adverse events will be coded using the Medical Dictionary for Regulatory Activities (MedDRA 17.1 or higher) and will be reported by primary system organ class (SOC) and PT.
- Safety laboratory testing including hematology, coagulation, serum chemistry, and urinalysis
- Vital signs
- Physical examinations
- ECG and/or ECHO

5.8.1 Adverse Events

In general, only TEAEs will be summarized (for untreated subjects, AEs that first occur or worsen in severity after the study enrollment are considered treatment-emergent). Non-treatment-emergent adverse events will be recorded in the data listings. Unless noted otherwise, for all AE tables, the number and percentage of patients reporting AEs will be grouped using the MedDRA, SOC, and PT and summarized for treated patients, untreated patients, and overall.

An overall summary table of adverse events will be produced and will include the frequency count and percentage of patients with

- TEAE
- Treatment-related TEAE
- Severe TEAE
- Treatment-Emergent SAE
- Treatment-Emergent Related SAE
- TEAE leading to discontinuation of study drug
- TEAE leading to death

The number of events at each severity level (mild, moderate, severe) will also be included.

Multiple occurrences of the same AE (at the PT level) in the same patient will be counted only once in frequency tables. If a patient experiences multiple episodes of the same event with a different relationship/severity, the event with the strongest relationship or maximum severity to investigational drug product will be used to summarize AEs by relationship and severity.

The following summary tables will be produced:

- TEAEs by SOC and PT
- TEAEs by SOC, PT and severity
- TEAE by PT in descending frequency
- Treatment-related TEAEs by SOC and PT
- Treatment-related TEAEs by SOC, PT, and severity
- Treatment-related TEAEs by PT in descending frequency
- Treatment-Emergent SAEs by SOC and PT
- Treatment-related Treatment-Emergent SAEs by SOC and PT
- TEAEs leading to treatment discontinuation by SOC and PT
- TEAEs leading to death by SOC and PT
- Non-serious TEAEs by SOC and PT, displaying both number of subjects and number of events

The following listings will be produced:

- All AEs
- AEs leading to treatment discontinuation
- SAEs

5.8.2 Adverse Events of Special Interest

Summaries of TEAEs of special interest will be summarized by SOC and PT. All standard MedDRA queries (SMQs based on MedDRA version 17.1) listed below will include broad and narrow terms. The AEs of special interest (AESI) are:

- Hypersensitivity (hypersensitivity SMQ)
- Renal toxicity (acute renal failure SMQ)
- Infusion-related reaction (IRR) (AEs occurring within 24 hours of the start of any infusion [including events that occurred on the same date as an infusion where infusion start time or AE onset time was not reported])

For all IRRs as defined above, adjudicated IRRs will be identified by a pharmacovigilance physician. All IRRs as defined above that are considered as related to study drug by investigators will be counted in the list of adjudicated IRRs. In addition, all

IRRs as defined above that meet the following criteria will be excluded from the list of adjudicated IRRs:

- AE was an infusion site, application site, or other local AE not associated with IRR
- AE had a clear alternate etiology that could be ascertained based on the reported event (eg, reaction to plaster, assessed as related to procedure or underlying disease by investigator)
- AE not associated with an IRR due to the nature of the event or biologically implausible (eg, fibula fracture, chalazion)

A summary table will be generated and include the following:

- Number of patients with adjudicated IRRs
- Number of adjudicated IRRs
- Number of adjudicated IRRs with event start time reported
- Number of events on any day for adjudicated IRRs

A corresponding listing will be generated for each table. Additionally, a table and listing corresponding to the AESIs that were related to study drug or moderate or severe will be produced.

An overall summary of AESI events will include the total number of events, number of serious events, number of related events, number of not related events, number of mild events, number of moderate events, number of severe events, and number of events occurring on the same day as an infusion.

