3. STUDY DESCRIPTION

3.1. Study Overview

This is an open-label, multi-center study to explore the safety and tolerability of eteplirsen in patients 4 to 6 years of age with genotypically-confirmed DMD with genetic mutations amenable to treatment by exon 51 skipping. An untreated group (DMD patients not amenable to exon 51 skipping) will be enrolled to further evaluate the natural history of DMD in this patient population.

Patients will be evaluated for inclusion during a Screening/Baseline period of up to 5 weeks. Eligible patients for the eteplirsen-treated group will receive once weekly IV infusions of 30 mg/kg eteplirsen for up to 96 weeks. An extension period may be considered prior to the end of the 96-week planned dosing period. Eligible patients for the untreated group (e.g., deletions of exons 44, 45, or 53) will not receive treatment of eteplirsen. Untreated patients will undergo select safety, functional, and laboratory assessments but will not provide blood samples for PK determination or undergo muscle biopsy procedures.

Safety will be assessed through the collection of adverse events (AEs)/serious AEs (SAEs), laboratory tests, electrocardiograms (ECGs), echocardiograms (ECHOs), vital signs, and physical examinations throughout the study.

Upon qualification for the study, patients enrolled into the eteplirsen-treated group will undergo the baseline assessments including a muscle biopsy, which may occur at a different study site (denoted as the surgical unit) than where patients will undergo infusions and study assessments (denoted as the infusion site). Eteplirsen-treated patients will be randomized to undergo a second muscle biopsy, scheduled at Week 48 or Week 96. CCI

Blood samples for population PK estimation will be collected from all eteplirsen-treated patients. Blood samples for serial PK estimation will be collected at select sites.

Following the end of the weekly infusions, patients will be required to return to the study site for End of Study safety evaluations.

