3.3. Sample Size and Power

Sample size for this study is based upon qualitative considerations; no formal sample size calculations will be performed. Up to 40 patients will be included in this study: approximately 20 patients in the eteplirsen-treated group (those amenable to exon 51 skipping) and up to 20 in the untreated control group (those not amenable to exon 51 skipping).

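### SAP 5.8.2 breaks down infusion-related reactions by type, severity and seriousness only for a timing-defined set; adjudicated reactions get counts and a listing but no such summary

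*SAP*

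**What the plan says.** SAP 5.8.2 lists three AESIs. Hypersensitivity and renal toxicity are defined by standard MedDRA queries. The third is defined by the clock: "Infusion-related reaction (IRR) (AEs occurring within 24 hours of the start of any infusion", with the extension "including events that occurred on the same date as an infusion where infusion start time or AE onset time was not reported". No term list or causality filter applies.

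Three outputs are then specified for AESIs without restriction to adjudicated events:

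- the SOC/PT tabulation: "Summaries of TEAEs of special interest will be summarized by SOC and PT";
- a table and listing of AESIs that were drug-related, or moderate, or severe;
- event counts: "An overall summary of AESI events will include the total number of events, number of serious events, number of related events"; unrelated events, each severity level and events on infusion days are counted too.

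The same section has a pharmacovigilance physician identify adjudicated reactions from the timing-defined set. Events the investigator calls drug-related are counted. Three groups are excluded: local events, events with a clear alternative cause, and the group described as "AE not associated with an IRR due to the nature of the event or biologically implausible", for which a fibula fracture and a chalazion are the examples. The table specified for the adjudicated set has four lines: patients, events, events with a reported start time, and events on any day. A listing accompanies each table.

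**The concern.** Safety and tolerability is the primary objective (SAP 2.1), and the drug is given by weekly infusion to boys aged 4 to 6. SAP 5.8 says the safety summaries will cover the type, frequency, severity, timing and relationship of adverse events. For infusion reactions, those breakdowns are specified on a set that the SAP itself expects to contain events that are not infusion reactions. The set cleaned of such events is counted and listed but not broken down. Both carry the label IRR, so a reader of the study report could take the SOC/PT and severity rows as a description of infusion reactions when they also describe coincidental childhood events.

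No other planned output lets the reader subtract the background. Untreated boys have no infusions and hence no window, and SAP 6.1 rules out direct comparison with them. No event rate for the other six days of the dosing week is planned.

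**Working it through.** The documents state no reaction rate, background event rate or adjudication yield, so there is no planned figure to reproduce. The size of the chance component can still be bounded.

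**Inputs from the documents.** Dosing: treated boys "will receive once weekly IV infusions of 30 mg/kg eteplirsen for up to 96 weeks" (SAP 3.1). Window: 24 hours from the start of each infusion (SAP 5.8.2). Treated patients: about 20 (SAP 3.3). Treatment-emergent period: first dose to 28 days after the last (SAP 4.8).

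**Assumptions.** Background events arise as a Poisson process at the same rate in every boy, onset is independent of infusion day, and all 96 infusions are given. The background rate and the true reaction rate are not in the documents, so both are shown as ranges.

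**Step 1: share of time in the window.** 24 h / 168 h = 96 days / 672 days = 14.3%, or 1 in 7. Over the whole treatment-emergent period of 95 × 7 + 28 = 693 days it is 96/693 = 13.9%.

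**Step 2: chance events per boy.** Mean m = rate × 96/365.25; P(at least one) = 1 − exp(−m).

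| Assumed background events per patient-year | m per boy | P(at least one) | Expected boys of 20 |
|---|---|---|---|
| 1 | 0.26 | 23% | 4.6 |
| 2 | 0.53 | 41% | 8.2 |
| 4 | 1.05 | 65% | 13.0 |
| 8 | 2.10 | 88% | 17.6 |
| 12 | 3.15 | 96% | 19.1 |

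Cross-check by count: a boy with k unrelated on-treatment events has chance 1 − (6/7)^k of at least one in the window. This is 54% for k = 5, 79% for k = 10 and 95% for k = 20.

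**Step 3: share of window events that is background.** With t true reactions per boy, the share is m/(m + t). At 4 background events per patient-year (m = 1.05):

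- t = 0.1: 91%
- t = 0.5: 68%
- t = 1: 51%
- t = 4: 21%

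Break-even is t = m, here about 1.05 true reactions per boy, or 1.05/96 = 1.1% of infusions. Over background rates of 1 to 12 and t from 0.1 to 4, the share runs from 6% to 97%.

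**Limits.** Closer observation on infusion days (Protocol 10.2 and 11.3.2: at least an hour's observation in the first year, with repeated vital signs) could push the share of recorded events above 1 in 7. Early discontinuation, or boys differing in their event rates, would lower the proportion of boys flagged at a given mean rate.

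**Step 4: the adjudication rule.** An infusion-site event judged drug-related by the investigator falls under the sentence that counts related events and also under the exclusion for local events. The text gives no order of precedence.

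**The case against.** The strongest defence is that this is a sensitive screen followed by medical adjudication, with both reported, and that over-inclusion errs towards disclosure. Much of that stands.

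Three stronger readings are tempting and are not supported:

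- *That the reported reactions are mostly chance.* This needs a background rate and a true reaction rate, and the documents give neither. Step 3 shows the answer can go either way.
- *That the reported incidence is only the raw one.* The number of patients with adjudicated reactions is the first line of the adjudicated table.
- *That true reactions are never characterised.* A listing accompanies the adjudicated table and is readable with about 20 treated boys. The AESI summary splits related from unrelated events. SAP 5.8.1 tabulates treatment-related events by SOC, PT and severity. Hypersensitivity is captured separately by term.

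It is also fair that the four lines are contents to be included, so more could be added, and that no test or error rate depends on these tables: SAP 5.8 is descriptive, and Protocol 14.1 treats any inferential statistics as descriptive only.

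The remaining gap is that none of these outputs is a summary of the adjudicated reactions. The related-or-moderate-or-severe table admits unrelated moderate and severe events and omits mild adjudicated events judged unrelated. The treatment-related tables follow investigator causality, not adjudication, and are not confined to the window.

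**Conclusion.** The point holds as a reporting gap. The specified type, severity, seriousness and relatedness summaries for infusion-related reactions rest on timing alone, and no specified table repeats them for the adjudicated set. Chance contamination is material: about 1 in 7 unrelated on-treatment events, and at assumed rates of 1 to 12 events per patient-year about 23% to 96% of boys with at least one. These figures rest on onset being independent of infusion day, a common Poisson rate and a full 96 weeks of dosing. The precedence conflict in the adjudication rule needs no assumption; it is in the text. Because adjudicated incidence and a listing are planned and nothing inferential depends on the tables, this is a cheap improvement and not a must-fix.

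**What to change.** In SAP 5.8.2:

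1. Produce the SOC/PT summary, the related-or-moderate-or-severe table and the overall summary (serious, related, severity) for adjudicated infusion-related reactions.
2. Keep the timing-based set alongside, retitled *AEs within 24 hours of infusion*. Optionally print the event rate on the remaining days of the dosing week, with a note that observation is closer on infusion days.
3. State which rule prevails when an investigator-related event also meets an exclusion criterion. Settle this before the adjudicated tables are run.

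The cost is SAP wording and some extra tables using a flag from an adjudication already planned; the optional rate needs a small extra calculation. The downside is that the adjudicated rows depend on one adjudicator's judgement in an open-label study, which is the reason to keep the timing-based table.
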